13.2.4 Investigator Compliance

No modifications to the protocol will be made without the approval of both the investigator and Vertex. Changes that significantly affect the safety of the subjects, the scope of the investigation, or the scientific quality of the study (i.e., PD assessments) will require IRB/IEC notification before implementation, except where the modification is necessary to eliminate an apparent immediate hazard to human subjects. Vertex will submit all protocol modifications to the required regulatory authorities.

When circumstances require an immediate departure from procedures set forth in the protocol, the investigator will contact Vertex to discuss the planned course of action. If possible, contact will be made before the implementation of any changes. Any departures from the protocol will be fully documented in the source documentation and in a protocol deviation log.

13.2.5 Access to Records

The investigator will make the office and/or hospital records of subjects enrolled in this study available for inspection by Vertex or its representative at the time of each monitoring visit and for audits. The records will also be available for direct inspection, verification, and copying, as required by applicable laws and regulations, by officials of the regulatory health authorities (FDA and others). The investigator will comply with applicable privacy and security laws for use and disclosure of information related to the research set forth in this protocol.

13.2.6 Subject Privacy

To maintain subject confidentiality and to comply with applicable data protection and privacy laws and regulations, all CRFs, study reports, and communications relating to the study will identify subjects by assigned subject numbers, and access to subject names linked to such numbers will be limited to the site and the study physician and will not be disclosed to Vertex. As required by applicable laws and regulations in the countries in which the study is being conducted, the investigator will allow Vertex and/or its representatives access to all pertinent medical records to allow for the verification of data gathered in the CRFs/SAE Forms and the review of the data collection process. The FDA and regulatory authorities in other jurisdictions, including the IRB/IEC, may also request access to all study records, including source documentation, for inspection.

For sites participating in the US, and in accordance with the Health Insurance Portability and Accountability Act (HIPAA) and associated regulations, an executed HIPAA authorization will be obtained by the site from each subject (or the legal representative of the subject) before research activities may begin. Each HIPAA authorization will comply with all HIPAA requirements including authorization allowing the site access to and use of the subject's personally identifiable health information, authorization for the site to disclose such information to Vertex, the FDA, and other parties requiring access under the protocol, and statements as to the purpose for which such information may be used and for how long.

13.2.7 Record Retention

The investigator will maintain all study records according to ICH GCP Guidelines and/or applicable local regulatory requirement(s), whichever is longest, as described in the Clinical Trial Agreement. If the investigator withdraws from the responsibility of keeping the study records, custody will be transferred to a person willing to accept the responsibility and Vertex will be notified.

13.2.8 Study Termination

At any time, Vertex may terminate this study in its entirety or may terminate this study at any particular site. In addition, for reasonable cause, either the investigators or their IRBs/IECs may terminate the study at their center.

Conditions that may lead to reasonable cause and warrant termination include, but are not limited to:

- Subject or investigator noncompliance
- Unsatisfactory subject enrollment
- Lack of adherence to protocol procedures
- Lack of evaluable and/or complete data
- Potentially unacceptable risk to study subjects
- Decision to modify drug development plan
- Decision by the FDA or other regulatory authority

Written notification that includes the reason for the clinical study termination is required.

13.2.9 End of Study

The end of study is defined as the last scheduled visit (or scheduled contact) of the last subject.

13.3 Data Quality Assurance

Vertex or its designated representative will conduct a study site visit to verify the qualifications of each investigator, inspect clinical study site facilities, and inform the investigator of responsibilities and procedures for ensuring adequate and correct study documentation.

The investigator is required to prepare and maintain adequate and accurate case histories designed to record all observations and other data pertinent to the study for each subject. Study data for each enrolled subject will be entered into a CRF by study site personnel using a secure, validated, web-based electronic data capture (EDC) application. Vertex will have read-only access to site-entered clinical data in the EDC application.

Instances of missing, discrepant, or uninterpretable data will be queried with the investigator for resolution. Any changes to study data will be made to the CRF and documented in an audit trail, which will be maintained within the clinical database.

13.4 Monitoring

Monitoring and auditing procedures developed or approved by Vertex will be followed to comply with GCP Guidelines. On-site or remote (as applicable by local regulation) checking of the CRFs/SAE Forms for completeness and clarity, cross-checking with source documents, and clarification of administrative matters will be performed.

The study will be monitored by Vertex or its designee. Monitoring will be done by personal or remote (as applicable by local regulation) visits from a representative of Vertex or designee (study site monitor), who will review the CRFs/SAE Forms and source documents. The study site monitor will ensure that the investigation is conducted according to the protocol design and regulatory requirements.

13.5 Electronic Data Capture

Vertex will provide the study sites with secure access to and training on the EDC application sufficient to permit study site personnel to enter or correct information in the CRFs on the subjects for which they are responsible.

A CRF will be completed for each enrolled study subject. It is the investigator's responsibility to ensure the accuracy, completeness, clarity, and timeliness of the data reported in the subject's CRF. Source documentation supporting the CRF data will indicate the subject's participation in the study and will document the dates and details of study procedures, AEs, other observations, and subject status.

The investigator, or designated representative, will complete the CRF as soon as possible after information is collected.

The audit trail entry will show the user's identification information and the date and time of any correction. The investigator will provide formal approval of all the information in the CRFs, including any changes made to them, to endorse the final submitted data for the subjects for whom the investigator is responsible.

[figure not shown]
Vertex will retain the CRF data and corresponding audit trails. A copy of the final archival CRF in the form of a compact disc (CD) or other electronic media will be placed in the investigator's study file.

13.6 Confidentiality and Disclosure

Any and all scientific, commercial, and technical information disclosed by Vertex in this protocol or elsewhere will be considered the confidential and proprietary property of Vertex. The investigator shall hold such information in confidence and shall not disclose the information to any third party except to such of the investigator's employees and staff as have been made aware that the information is confidential and who are bound to treat it as such and to whom disclosure is necessary to evaluate that information. The investigator shall not use such information for any purpose other than determining mutual interest in performing the study and, if the parties decide to proceed with the study, for the purpose of conducting the study.

The investigator understands that the information developed from this clinical study will be used by Vertex in connection with the development of the study drug and other drugs and diagnostics, and therefore may be disclosed as required to other clinical investigators, business partners and associates, the FDA, and other government agencies. The investigator also understands that, to allow for the use of the information derived from the clinical study, the investigator has the obligation to provide Vertex with complete test results and all data developed in the study.

13.7 Publications and Clinical Study Report

[figure not shown]
13.7.2 Clinical Study Report

A CSR, written in accordance with the ICH E3 Guideline, will be submitted in accordance with local regulations.

Protocol Number: VX19-864-101

4 INTRODUCTION

All analysis outputs (tables, figures, listings, and datasets) will be generated using SAS® Version 9.4 or higher (SAS Institute, Cary, North Carolina, USA).

The SAP (Methods) will be finalized and approved before the clinical database lock. Any revisions to the approved SAP will be documented and approved in an amendment to the SAP prior to the clinical database lock. Any revisions made to the SAP after the clinical database lock will be documented in the clinical study report for this study.

The analysis addressing the pharmacokinetic (PK) objective of the study will be described in the Clinical Pharmacology Analysis Plan (CPAP) which will be developed separately by the Clinical Pharmacology department at Vertex.

5 STUDY OBJECTIVES

5.1 Primary Objectives

- To evaluate the efficacy of VX-864 in *PiZZ* subjects as measured by plasma functional alpha-1 antitrypsin (AAT) levels
- To evaluate the safety and tolerability of VX-864 in *PiZZ* subjects

5.2 Secondary Objectives

- To evaluate the efficacy of VX-864 in *PiZZ* subjects as measured by plasma antigenic AAT levels
- To evaluate the pharmacokinetics (PK) of VX-864 in *PiZZ* subjects

6 STUDY ENDPOINTS

6.1 Primary Endpoints

- Change from baseline in plasma functional AAT levels at Day 28
- Safety and tolerability assessments based on adverse events (AEs), clinical laboratory values, standard 12-lead ECGs, vital signs, and pulse oximetry

6.2 Secondary Endpoints

- Change from baseline in plasma antigenic AAT levels at Day 28
- PK parameters of VX-864 derived from plasma concentration-time data

7 STUDY DESIGN

7.1 Overall Design

This is a Phase 2, randomized, double-blind, placebo-controlled study of VX-864. Schematics of the study design are shown in Figure 7-1 and Figure 7-2.

Approximately 40 subjects in total with the PiZZ genotype and antigenic AAT levels <8 μ M at screening will be randomized to VX-864 or placebo 2:1:1:1 to VX-864 500 mg q12h, VX-864 300 mg q12h, VX-864 100 mg q12h, or placebo.

[figure not shown]
Of these, approximately 20 subjects will be randomized 2:2:1 to VX-864 500 mg q12h, VX-864 300 mg q12h, or placebo first. The remaining subjects (approximately 20) will be randomized

Vertex Pharmaceuticals Incorporated

2:2:1 to VX-864 500 mg q12h, VX-864 100 mg q12h, or placebo. Randomization will be stratified by post-bronchodilator percent predicted forced expiratory volume in 1 second (ppFEV₁) obtained either during the Screening Period or from a historical post-bronchodilator ppFEV₁ value measured within 1 year before screening (<50% versus $\ge50\%$).

Screening assessments for subjects who have never been on augmentation therapy are listed in Table 3-1 of the protocol. Screening assessments for subjects who have been on augmentation therapy at any time are listed in Table 3-2 of the protocol. Treatment Period assessments for all subjects are listed in Table 3-3 of the protocol.

[figure not shown]
Figure 7-1 Schematics of Study Design for Subjects Who Have Never Been on Augmentation Therapy

AAT: alpha-1 antitrypsin; N: number of subjects; q12h: every 12 hours

Notes: Figure is not drawn to scale. Subject numbers include subjects who have never been on augmentation therapy and subjects who have been on augmentation therapy at any time. Antigenic AAT levels must be drawn to confirm eligibility and sent to the central laboratory; results must be obtained and confirmed to be <8 µM before randomization. Once antigenic AAT levels have been confirmed to meet this eligibility criterion, randomization and Day 1 can occur any time within the remaining screening window. Sites should allow at least 14 days for sample processing and antigenic AAT level result reporting.

Figure 7-2 Schematics of Study Design for Subjects Who Have Been on Augmentation Therapy at Any Time

AAT: alpha-1 antitrypsin; N: number of subjects; q12h: every 12 hours

Notes: Figure is not drawn to scale. Subject numbers include subjects who have never been on augmentation therapy and subjects who have been on augmentation therapy at any time. Subjects must discontinue augmentation therapy >42 days before antigenic AAT levels are drawn and sent to the central laboratory to confirm eligibility; results must be confirmed to be <8 μM before randomization. Once antigenic AAT levels have been confirmed to meet this eligibility criterion, randomization and Day 1 can occur any time within the remaining screening window. Sites should allow at least 14 days for sample processing and antigenic AAT level results reporting. Subjects can resume augmentation therapy after completion of assessments at the last Safety Follow-up Visit.

[figure not shown]
*Blood samples will be obtained for antigenic and functional AAT levels at the same time that the other screening laboratory assessments are performed. If the subject received the last dose of augmentation therapy >42 days prior, this sample can be used to measure antigenic AAT level for eligibility. If samples are obtained <42 days after the last dose of augmentation therapy, another sample **must** be drawn >42 days after the last dose of augmentation therapy and sent to the central laboratory to confirm eligibility.

[figure not shown]
7.2 Sample Size and Power

Subjects will be randomized 2:1:1:1 to receive VX-864 500 mg q12h (n = 16), VX-864 300 mg q12h (n = 8), VX-864 100 mg q12h (n = 8), or placebo (n = 8).

Assuming 10% of the randomized subjects have a missing value at Day 28, this sample size provides adequate precision to estimate the absolute plasma functional AAT levels at Day 28 for the VX-864 500 mg q12h dose group.

Information regarding the sample size assessments is provided below.

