9 STATISTICAL ANALYSIS

9.1 General Considerations

The Schedule of Assessments is provided in Section 3 of the CSP. The precision standards for reporting safety variables are provided in an internal Biometrics document that specifies programming rules including the precision for derived variables.

Continuous variables will be summarized using the following descriptive summary statistics: the number of subjects (n), mean, SD, median, minimum value (min), and maximum value (max).

Categorical variables will be summarized using counts and percentages.

Baseline value, unless specified otherwise, will be defined as the most recent non-missing measurement (scheduled or unscheduled) collected before the first dose of study drug. For

ECGs, the baseline value will be defined as the average of the non-missing pre-dose measurements (triplicate) collected before the first dose of study drug. For subjects who have ever been on augmentation therapy at any time, only functional and antigenic AAT levels collected >42 days after the last dose of augmentation therapy can be used to define baseline values. For antigenic AAT levels, only the screening results obtained from the on-treatment assay can be used to define baseline values if the Day 1 pre-dose results are missing.

Change (absolute change) from baseline will be calculated as post-baseline value – baseline value.

Relative change from baseline will be calculated and expressed in a percentage as $100\% \times (\text{post-baseline value} - \text{baseline value})$ /baseline value.

Treatment-emergent (TE) Period will include the time period starting from the date of the first dose of study drug to either (1) Safety Follow-up Visit 28 days after the last dose of study drug, (2) Early Termination of Treatment (ETT) Visit if it replaces the Safety Follow-up Visit 28 days after the last dose of study drug, or (3) 28 days after the last dose date for subjects who do not have a Safety Follow-up Visit 28 days after the last dose or an equivalent ETT.

Unscheduled visits: Data obtained from unscheduled visits will be included in the analysis as follows:

- In scheduled visit windows per specified visit windowing rules
- In the derivation of baseline and last on-treatment measurements
- In the derivation of maximum and minimum values during the TE period, and maximum and minimum change from baseline values during the TE period for safety analyses
- In individual subject data listings as appropriate

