9.3.1.2 Primary Analysis

The primary analysis of the primary efficacy variable includes data from VX-864 treatment groups and the placebo group. The primary comparison consists of the pairwise comparison between each dose of VX-864 and placebo.

The primary analysis will be based on a mixed-effects model for repeated measures (MMRM) with change from baseline at Days 7, 14, and 28 as the dependent variable. The MMRM model will include the treatment group, visit, and treatment-by-visit interaction as fixed effects. An unstructured covariance structure will be used to model the within-subject errors. If the model estimation does not converge, a compound symmetry covariance structure will be used instead. The model will be estimated using restricted maximum likelihood. Denominator degrees of freedom for the F-test for fixed effects will be estimated using the Kenward-Roger approximation. Conditional on the observed data and covariates, missing data will be assumed to be missing at random; consequently, no imputation of missing data will be performed.

The primary result obtained from the model will be the estimated treatment difference between each VX-864 treatment group in the model and the placebo group at Day 28. The adjusted means with 2-sided 95% confidence intervals and 2-sided *P* values will be provided. In addition, the estimated treatment differences, obtained from the model, between each VX-864 treatment group

in the model and the placebo group at each post-baseline visit will be provided, along with 2-sided 95% confidence intervals and 2-sided *P* values.

The observed values and change from baseline of functional AAT levels will also be summarized descriptively by treatment group at each visit.

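### Does sizing the trial on the absolute Day 28 level in the 500 mg arm leave the primary comparison with placebo without support?

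*SAP*

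**What the plan says.** SAP 7.2 and protocol 12.1 allocate 16 subjects to 500 mg q12h and 8 each to 300 mg, 100 mg and placebo. The justification is one of precision, not power. It allows for dropout ("Assuming 10% of the randomized subjects have a missing value at Day 28") and then asserts, with reference to the 500 mg arm alone, that "this sample size provides adequate precision to estimate the absolute plasma functional AAT levels at Day 28". Both sections then say "Information regarding the sample size assessments is provided below", but no SD, half-width or power figure follows in the public text.

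SAP 9.3.1.2 analyses change from baseline at Days 7, 14 and 28 with an MMRM. It states: "The primary result obtained from the model will be the estimated treatment difference between each VX-864 treatment group" and placebo at Day 28, with 95% intervals and P values. Adjusted means also get 95% intervals, but the model is for change, so these are mean changes. For absolute levels: "The observed values and change from baseline of functional AAT levels will also be summarized descriptively by treatment group at each visit". SAP 9.1 defines that summary ("Continuous variables will be summarized using the following descriptive summary statistics") as n, mean, SD, median, minimum and maximum. It also states that missing data are not imputed unless specified otherwise. SAP 9.3.3 applies no multiplicity adjustment.

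**The concern.** The quantity used to size the trial and the quantity called primary differ in three ways: level against change, one arm against a contrast, and the largest arm against comparisons limited by 8 placebo subjects. A reader could take the assurance of adequate precision to cover the primary result, although the visible sentence does not address it.

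The sized quantity also has no planned interval in the visible SAP. Its mean will come from subjects with a Day 28 value, whereas the MMRM also draws on Days 7 and 14. If this mattered, the trial would be sized for an estimate it does not formally report, and its primary differences could be much less precise than readers expect.

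**Working it through.** **Arm sizes.** These are the only figures in the statement that can be reproduced.
- 2:1:1:1 of 40: 40 × 2/5 = 16 and 40 × 1/5 = 8 for each other arm.
- Two cohorts of 20 at 2:2:1: 500 mg 8 + 8 = 16; 300 mg 8; 100 mg 8; placebo 4 + 4 = 8.
- With 10% missing at Day 28: 0.9 × 16 = 14.4 and 0.9 × 8 = 7.2, in total 36.

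The arm sizes agree with each other. The phrase about adequate precision cannot be reproduced, because no SD or target half-width is visible.

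**Half-widths in SD units.** Assumption: one SD for all arms and for both level and change; completers only; pooled t on 36 − 4 = 32 df (2.037).
- 500 mg mean: 2.037/√14.4 = 0.54 SD. With that arm's own 13.4 df it is 2.154/√14.4 = 0.57 SD.
- 500 mg minus placebo: 2.037 × √(1/14.4 + 1/7.2) = 0.93 SD.
- 300 or 100 mg minus placebo: 2.037 × √(2/7.2) = 1.07 SD.

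With the same critical value throughout, the differences are √3 = 1.73 and 2.0 times as wide as the 500 mg mean. Using the arm's own df for the mean gives 0.930/0.568 = 1.64 and 1.074/0.568 = 1.89.

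**Detectable difference.** For 80% power at two-sided 5%, the normal approximation gives 1.28 SD (500 mg) and 1.48 SD (lower doses). The noncentral t gives 1.32 and 1.52 SD.

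**Effect of the common-SD assumption.** Level and change need not share an SD. Let ρ be the correlation between baseline and Day 28, with equal SD at both times, so that SD(change) = SD(level) × √(2(1 − ρ)). Let k be the placebo SD divided by the 500 mg SD. The ratio of the 500 mg minus placebo half-width (change) to the 500 mg half-width (level) is

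√(2(1 − ρ)) × √(1 + 2k²).

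| ρ | k = 1 | k = 0.5 |
|---|---|---|
| 0 | 2.45 | 1.73 |
| 0.5 | 1.73 | 1.22 |
| 0.7 | 1.34 | 0.95 |
| 0.83 | 1.00 | 0.71 |
| 0.9 | 0.77 | 0.55 |

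The documents give neither ρ nor k. The difference may be estimated much less precisely than the level, about as precisely, or more precisely.

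**Cost of sizing on the difference.** Under the common SD, giving the 500 mg difference the precision of the 500 mg mean at 2:1 needs 1.5/n = 1/14.4. That is n = 21.6 placebo and 43.2 treated completers, or 24 and 48 randomized instead of 8 and 16.

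**What the planned outputs already give.** The 500 mg interval at Day 28 is mean ± t × SD/√n, and all three inputs are in the planned table. The differences have 95% intervals from the MMRM.

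**The case for a change.** The strongest case for acting is that a trial sized on the precision of one quantity should specify that quantity's interval and say how missing values enter it. The plan should also say what precision the primary differences will have. Two of the three primary comparisons involve only arms of 8, the study is meant to help identify a dose, and the remedy costs one table column and one sentence. That the SDs are unknown makes the request stronger, since precision for a level does not establish precision for a difference in change.

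Part of this stands. The visible justification does not cover the primary comparison, and no interval for the level is visible. An interval in the descriptive table would be a harmless convenience.

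The rest does not require an amendment. A missing-data rule for the level exists: the general no-imputation rule in SAP 9.1. The sizing sentence is limited to the 500 mg arm and makes no visible claim of power or precision for the differences, so no stated figure is wrong. The sample size detail announced in both documents is absent from the public text, and text is redacted after the MMRM description in the protocol synopsis and in 12.3.3.1. Either gap may hold what is being asked for. A second MMRM on levels with baseline as a covariate would not supply the sized quantity either. Its adjusted means refer to a common baseline, not to the 500 mg arm's own level, and it would add a rival estimate of the dose-placebo differences.

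**Conclusion.** No change is needed. The sizing statement and the primary analysis address different quantities, but nothing stated is shown to be wrong. Giving the double share to 500 mg fits a precision target set in that arm, and sizing on a precise single-arm estimate is a fair trade-off in a Phase 2 study of about 40 subjects. Followed as written, the plan yields an interval for each dose-placebo difference and the three figures from which the 500 mg level interval follows. Any lack of precision against placebo will be visible in the reported intervals.

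Under a common SD, 10% missing and completers only, the differences are about 1.7 times (500 mg) and 2.0 times (300 or 100 mg) as wide as the 500 mg mean. For 500 mg with equal arm SDs the multiple falls below 1 once the baseline to Day 28 correlation exceeds about 0.83. The completer counts are an approximation, since the MMRM also uses subjects with only Day 7 or Day 14 values. The statement that no interval for the level and no precision figure for the differences is planned holds for the visible text only.
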